6.1.2.4 Scientific Steering Committee

A scientific steering committee will be established and responsible for the quality and successful implementation of the overall program. It will consist of external asthma experts and investigators. The Scientific Steering Committee duty include:

- To deliver lecture as a speaker at initial comprehensive education
- To advise the sponsor on amendments to the study design and provide recommendations on issues related to the study conduct, if required.

6.1.2.5 Dedicated Qualified Team to Deliver Initial Comprehensive Education

Initial comprehensive education will be delivered at each participating hospital by a dedicated qualified team, immediately after last patient enrolled at each site. The major topics will be delivered by asthma expert in the same province or in the same region of the participating hospital.

6.2 Preparation/Handling/Storage/Accountability

Not applicable.

6.3 Study Intervention Compliance

Please refer to section 6.1.2.3 Guideline Implementation Performance Assessment with Feedback and Adjustment. Pulmonologists' guideline implementation performance will be assessed monthly based on pre-defined key performance indicator (KPI) and give feedback to the PI of the respiratory department of participating hospital.

6.4 Concomitant Therapy

Medication not related to asthma that the participant is receiving at the time of enrolment or receives during the study will not be recorded, except for systemic or oral steroids, with its medical rationale.

The Study Physician should be contacted if there are any questions regarding concomitant or prior therapy.

6.5 Dose Modification

Not applicable.

6.6 Intervention After the End of the Study

Not applicable.

6.7 Study Bias and Mitigation Plan

A single-arm design is chosen for its potential benefit to recruit more patients into an interventional arm instead of being randomized into a control arm. Before-intervention and post-intervention change will be described within individuals, which will reduce the variability. However, since single-arm studies do not include a direct, concurrent comparison group, their role in informing comparative effectiveness questions is not straightforward. The observed change might be impacted by the factors other than the intervention. This study might be subject to Hawthorne effect, e.g., pulmonologists and patients might change their behavior solely as a result of knowing that they are participating a study and being observed rather than as a result of the intervention. This may present a challenge to result interpretation.

There may be a hospital and patient selection bias, e.g., potential hospitals and patients can refuse to participate in this study leading to impact on the representativeness of the target hospitals and patient population. A total of around 30 hospitals will be selected in this study. To represent the diversity of patients, pulmonologists, and treatment practice in real world, hospital selection will include as many as provinces or municipalities in mainland China, where the altitude is below 1,500 meters, while balancing hospital grade (e.g. 10 Tier 2 and 20 Tier 3). Patients will be recruited in hospital outpatient setting. To minimize patient selection bias, all potentially eligible asthma patients will be consecutively approached and invited to join the study, e.g., regardless of new patients or treated, exacerbation or regular follow-up. The hospital selection and patient enrolment process will be appropriately documented.

Prior to the study intervention, there is 3-month patient recruitment period. During the 3 months, patients' health status may change and they may seek medical care due to asthma. These changes will not be captured in this study.

The intervention will be targeting pulmonologists at site hospitals. To reflect the real world practice, all pulmonologists attending outpatient clinics will be expected to recruit patients. However, depending on the scale of the selected hospitals and actual study operation, the number of participating pulmonologists will vary, as well as the number of pulmonologists who recruit patients, and the number of patients recruited per pulmonologists. These variations may introduce biases into this study. During the study conduct, patient recruitment will be closely monitored for unusual pattern. In addition, the statistical analyses will take into account the within-hospital and within-pulmonologist correlation, by including the hospital and pulmonologist effect into the model as random effect.

Retrospective data based on electronic medical records (EMR) offers a potential source of data collection. However, the original purpose of collecting EMR is for clinical care

management rather than research purpose, so there are inherent limitations in using EMR data to conduct clinical research, e.g., information incompleteness and data inaccuracy. Some data required by the protocol, e.g., ACQ-5 and AQLQ(S)+12, are not routinely collected in clinical practice. As this is a pragmatic study, patients can potentially go to any hospitals or pulmonologists for care during the study and EMR data from site hospitals will not be able to capture all the information. Given these inherent limitations of EMR data, we choose to prospectively collect data from patients in this study.

For data collection in this study, there are a few sources. For example, baseline clinical characteristics information will be based on patients self-reporting. During the study, patients may seek care in a hospital other than the study hospital, which may lead to missing data or inconsistency in data collection. The multiple data sources may introduce inconsistencies in the data and affect the data quality. To minimize the impact, firstly, for baseline data collection, data on treatment pattern and PROs, baseline data will be collected during V0; data on hospitalization due to exacerbation history will also require participating patients to provide evidence, e.g., medical records. Participating patients will be encouraged to visit study participating hospitals if feasible. On the other hand, if participating patients seek care in hospitals other than the study hospital, then data will be collected based on patient-provided hospital medical records.

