1.3 Schedule of Activities

Table 1 Schedule of Activities (participating patients related)

Study Visit	Baseline Period	Intervention Period					Details in CSP Section or Appendix
		V1	V2	V3	V4	V5 (Study completion/ withdrawal)	
Weeks	V0	-12 ± 7	0 ± 14	12 ± 7	24 ± 7	36 ± 7	48 ± 7
Informed consent ^a	X						
Inclusion and exclusion criteria	X						Sections 5.2.1 and 5.2.2. 2
Demographics ^b	X						
Vital Sign ^c	X						
Subject status ^d	X						
Smoking status ^e	X						
Medical history (comorbidities) and medications ^f	X						
Asthma history & related treatment ^g	X						
Severe asthma exacerbation		X	X	X	X	X	
Hospitalization due to asthma exacerbation since last visit		X	X	X	X	X	Section 8.1.4
ACQ-5	X	X	X	X	X	X	Section 8.1.5.1
AQLQ(S)+12	X	X	X	X	X	X	Section 8.1.5.2
PFT	X					X	
MARS-A questionnaire	X		X	X		X	
Questionnaire of asthma knowledge for patient	X		X	X		X	
Inhale skill score for patient		X	X	X		X	

Study Visit	Baseline Period	Intervention Period					Details in CSP Section or Appendix
		V1	V2	V3	V4	V5 (Study completion/ withdrawal)	
Patient's expectation for asthma treatment	X		X	X		X	
Laboratory assessments within prior 3 months (if available in medical records) ^h	X	X	X	X	X	X	
PFT/BPT/PEF/FeNO within prior 3 months (if available in medical records)	X	X	X	X	X	X	
Medical records on asthma related assessment and treatment	X	X	X	X	X	X	
Questionnaire for Asthma Patients during COVID-19 ⁱ	X						Section 8.1.9
Patient evaluation on whose pulmonologists 1. assess symptom control, 2. watch the patient using their inhaler, educate their technique, 3. have a discussion about adherence, 4. develop or review the written asthma action plan, provide patient education, 5. had a PFT before dosage reduction	X	X	X	X	X	X	Section 6.1.2.3

PFT = Pulmonary Function Testing; BPT = Bronchial provocation test; PEF = Peak expiratory flow; FeNO = Fractional exhaled nitric oxide

- a. Informed consent must be conducted prior to performing any study procedures including data collection.
- b. Demographic includes patient age, gender, race, ethnicity and
- c. Vital signs include body mass index (BMI, calculation by height and weight)
- d. Subject Status education level, family monthly income, job, residence (urban communities or rural villages), etc
- e. Smoking status include current smoker or stopping smoking or restarting smoking, smoking pack-years

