At follow-up visits (V1 to V5), the data generated from usual care activities after the initiation of the intervention will be collected from patients, including severe asthma exacerbation, asthma-related hospitalizations, emergency attendances, and outpatient visits, and medications.

In addition, two PRO questionnaires (ACQ-5 and AQLQ(S)+12) will be administered to participants at site at each visit and be entered by study personnel into the EDC system. MARS-A questionnaire, Questionnaire of asthma knowledge for patient, Inhale skill score for patient,

Patient's expectation for asthma treatment will also be administered.

The schedule of assessments and procedures are summarized in Table 1.

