4.1.1 Subject Disposition and Completion Status

The number of subjects who signed the informed consent will be calculated.

The number and percentage of subjects who enrolled, completed the study, remained on study and withdrew early will be summarized. The number and percentage of subjects who withdrew early for various reasons will be summarized according to the categories in the CRF. Study follow-up time and primary reason for screen failure will be summarized. Listing will also be presented.

Study Follow-up Time = EOS – training date +1

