5 INTERIM ANALYSIS

There will be two interim analyses, first interim analyses will mainly focus on the baseline when all subjects enrolled and finish baseline assessment, and the other will happen when all subjects complete week 12 visit.

First interim analysis includes the following parts:

1. Subject disposition
2. Demographics
3. Substance use – nicotine
4. Asthma history
5. Historical asthma exacerbation
6. Prior and concomitant medications – asthma/asthma related comorbidities
7. Prescribed medication – asthma
8. ICS-based maintenance and/or reliever treatment
9. ACQ-5 average scores
10. Distribution of ACQ-5 average scores (Well controlled/Partly controlled/Not well-controlled) and its subgroup listed in Section 4.2.3.12
11. ICS-formoterol as reliever
12. Asthma treatment patterns
13. Numbers of severe asthma exacerbation
 - a. With ICS containing vs. without ICS containing
 - b. Good adherence vs. not
14. Health-related quality of life evaluated by Asthma Quality of Life Questionnaire for 12 years and older (AQLQ(S)+12) score
15. MARS-A average score
16. Hematology

17. Blood Gas
18. IgE
19. FeNO
20. Pulmonary Function Test (PFT)
21. Pulmonary Function Test-Post-BDT (PFT)

Second interim analysis includes the following parts:

1. Subject disposition
2. Demographics
3. Substance use – nicotine
4. Asthma history
5. Historical asthma exacerbation
6. Prior and concomitant medications – asthma/asthma related comorbidities
7. Prescribed medication – asthma
8. ICS-based maintenance and/or reliever treatment
9. ACQ-5 average scores
10. Distribution of ACQ-5 average scores (Well controlled/Partly controlled/Not well-controlled) and its subgroup listed in Section 4.2.3.12
11. ICS-formoterol as reliever
12. Asthma treatment patterns
13. Patient evaluation on whose pulmonologists (whether their pulmonologists develop or review the written asthma action plan and watch the patient using their inhaler, checking their technique)
14. Numbers of severe asthma exacerbation
 - a. With ICS containing vs. without ICS containing
 - b. Good adherence vs. not

15. Health-related quality of life evaluated by Asthma Quality of Life Questionnaire for 12 years and older (AQLQ(S)+12) score
16. MARS-A average score
17. Inhaler skill score of subjects
18. Asthma knowledge score of subjects
19. Patient expectations of asthma treatment
20. Asthma knowledge questionnaire score of investigators
21. Adverse event
22. Hematology
23. IgE
24. FeNO
25. Pulmonary Function Test (PFT)

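### Protocol 6.7 and section 8 exclude events before the programme starts, but the Schedule of Activities records them at V1, and no disclosed SAP rule sorts exacerbations by training date

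*Protocol*

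**What the plan says.** Three places in the protocol bear on what is recorded between enrolment and training.

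- Section 6.7 describes the gap: "Prior to the study intervention, there is 3-month patient recruitment period". It continues: "During the 3 months, patients' health status may change and they may seek medical care due to asthma". It then closes the matter: "These changes will not be captured in this study".
- Section 8, under follow-up data collection, states that at V1 to V5 "the data generated from usual care activities after the initiation of the intervention will be collected from patients, including severe asthma exacerbation", and goes on to name hospitalizations as well.
- The Schedule of Activities (section 1.3, repeated in SAP 1.2) places V0 at week -12 and V1 at week 0. It marks "Severe asthma exacerbation" and "Hospitalization due to asthma exacerbation since last visit" at V1 to V5 and leaves both blank at V0.

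The synopsis and section 8 both call V1 a follow-up visit, and the schedule puts it under the intervention period.

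The SAP uses two anchors. Section 4.1.1 defines "Study Follow-up Time = EOS – training date +1". Section 3.1.3 counts study day from Visit 1 and gives events before Visit 1 a negative day. Section 5 lists "Numbers of severe asthma exacerbation" as an output of both interim analyses. The exploratory endpoint sections are blank in the public version.

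**The concern.** At V1 the last visit is V0, so the hospitalization row asks about the very weeks that section 6.7 says are not captured and that section 8 leaves out. A site that follows the schedule would enter roughly 12 weeks of pre-training hospitalizations at V1. A site that follows the text would enter few or none. The severe exacerbation row states no recall period and can be read either way.

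Two things are at stake. First, pre-training events can end up among records labelled follow-up, and if they are counted as such, events from before the programme are charged to it. Second, a collection rule that differs between sites cannot be repaired in the analysis, because events a site did not record cannot be recovered. The protocol expects the programme to reduce disease burden and has no control arm, so the boundary between before and after training needs to be clean for every outcome counted over time.

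**Working it through.** **Inputs.** V0 at week -12 (± 7 days) and V1 at week 0 (± 14 days), from the Schedule of Activities. Follow-up of 48 weeks and total participation of about 60 weeks, from protocol 4.1. Training follows the last enrolment at each site, also from 4.1.

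**1. Reproduce the stated duration.** 12 + 48 = 60 weeks, which matches protocol 4.1. The V0-to-week-0 interval is therefore part of the planned participation time but not of the 48 weeks of follow-up.

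**2. Period covered at V1 by a since-last-visit record.**
- Nominal: 0 - (-12) = 12 weeks (84 days), all before week 0.
- V0 to week 0 with the V0 window: 84 ± 7 = 77 to 91 days, or 11 to 13 weeks.
- V0 to V1 with both windows: shortest -14 - (-77) = 63 days; longest 14 - (-91) = 105 days; that is 9 to 15 weeks.

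**3. What section 8 leaves to record at V1.** With V1 on its nominal day there is no time after initiation. With V1 at +14 days and V0 at week -12, the record spans 84 + 14 = 98 days, of which 84/98 = 86% precede week 0. So the two instructions cover largely different periods at this visit.

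**4. Can the disclosed SAP separate the events?** Study day (3.1.3) is tied to Visit 1. Follow-up time (4.1.1) is tied to the training date. The Week 0 analysis window (3.1.4) opens on the training day and runs to D42. A V1 record can therefore mix events from before and after training, and visit number alone does not separate them. For prescriptions, SAP 4.1.9 does deal with the gap: week 12 counts only those from Visit 1 onward, and later visits count only those after the preceding visit. No parallel rule for exacerbations is visible.

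**5. Hypothetical size.** Suppose the event rate is constant, every V1 to V5 event is counted, and the total is divided by time since training. With a gap of g weeks from V0 to training:

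ratio = (g + 48)/48

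- g = 12 (nominal maximum): 60/48 = 1.25, an overstatement of 25%.
- g = 6 (assumed average: even accrual over three months, training straight after the last enrolment): 54/48 = 1.125, an overstatement of 12.5%.
- g = 13 (outer edge of the V0 window): 61/48 = 1.27.

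On the nominal schedule, 12/60 = 20% of the time covered by V1 to V5 precedes training.

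**The case against.** The case against is substantial.

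- Sections 6.7 and 8 agree with each other, and the explicit conflict comes from one schedule row. Only the hospitalization row carries the since-last-visit wording. For severe exacerbation, reading the V1 entry back to V0 is an inference, though at week 0 little else could be recorded, and the definition in 8.1.5 includes hospitalization. This narrows the contradiction but does not remove it.
- Section 6.7 is a paragraph on limitations, not a collection instruction. True, but section 8 is an instruction and says the same.
- SAP 3.1.3 already places dated events relative to Visit 1. This stands, and the gap is smaller than if nothing existed. It does not classify by training date.
- Sites work from eCRF instructions and a CRF that are not public, and these may settle the recall period. So differing site practice is a possibility the protocol leaves open, not an observed fact.
- No disclosed endpoint divides exacerbations by time since training. The 4.1.1 follow-up time sits in the disposition summary and is not stated as a denominator for events.
- A pre-study exacerbation history over 12 months is already collected. It is retrospective, but it means the V0-to-training period is not the only information on earlier events.
- A pre/post comparison of event rates would be a new analysis with its own bias, since patients are enrolled when they attend for care, some of them during an exacerbation.

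A reader might infer that the trial's exacerbation result is biased by 25%, or that half of the event time at the second interim (12 of 24 weeks) is wrongly credited to the programme. The documents do not support either. The interim item is a count split by ICS use and adherence, not by period, and it also appears at the first, baseline-focused interim. The redacted exploratory text may sort the events correctly.

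**Conclusion.** The collection rules conflict in the current text: 6.7 and section 8 exclude the pre-training period, while the schedule includes it for hospitalization at V1 and leaves it undefined for severe exacerbation. As written, up to about 12 weeks of pre-training events can enter follow-up records, and how many may depend on the site. The figure is nominal: the V0 window allows 13 weeks, and patients enrolled late at a site have a shorter gap.

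The primary endpoint and the disclosed secondary endpoints are not affected; they rest on prescriptions dated by SAP 4.1.9 and on ACQ-5. The exposure is confined to exacerbation and hospitalization summaries, including the severe exacerbation count at the second interim. The 25% and 12.5% are ceilings under a calculation that the disclosed SAP does not specify, with a constant rate assumed. An error of that kind would count against the programme and would not create a false benefit.

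This is worth correcting because a later analysis rule cannot restore events that were never recorded. It does not put the main result in doubt.

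**What to change.** Reconcile protocol 6.7, section 8 and the Schedule of Activities (and its copy in SAP 1.2). State one recall period for V1, since V0, for both severe exacerbation and hospitalization, with an onset date for each event.

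In the SAP, classify each event by onset date against the site training date. Count as post-intervention only events on or after training, over time since training, at the second interim and in the final analysis. If the redacted text already contains such a rule, a cross-reference is enough.

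Events from V0 to training may be reported descriptively as a separate period with their own person-time. That table should carry a caution that patients were enrolled when seeking care, so a fall from that period may reflect regression to the mean and is not evidence of a programme effect.

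The cost is protocol wording, an eCRF completion note and one SAP derivation. The V1 visit and both V1 entries are already in the schedule. Where V1 visits have already taken place, the sponsor should establish which recall period each site used.

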7 DISCONTINUATION OF STUDY INTERVENTION AND PARTICIPANT DISCONTINUATION/WITHDRAWAL

7.1 Discontinuation of Study Intervention

Not applicable.

7.2 Participant Withdrawal from the Study

- A participating patient may withdraw from the study at any time at his/her own request, or may be withdrawn at any time at the discretion of the investigator for safety, behavioural, compliance, or administrative reasons.
- A participating patient who considers withdrawing from the study must be informed by the investigator about modified follow-up options (e.g., telephone contact, a contact with a relative or treating pulmonologists, or information from medical records).
- At the time of withdrawal from the study, if possible, an Early Study Discontinuation visit should be conducted, as shown in the SoA. See SoA for data to be collected at the time of study withdrawal and follow-up and for any further evaluations that need to be completed.

- If the participating patient withdraws consent for disclosure of future information, the sponsor may retain and continue to use any data collected before such a withdrawal of consent.

7.3 Lost to Follow up

A participating patient will be considered lost to follow-up if he or she repeatedly fails to return for scheduled visits and is unable to be contacted by the study site.

The following actions must be taken if a participating patient fails to return to the clinic for a required study visit:

- The site must attempt to contact the participating patient and reschedule the missed visit as soon as possible and counsel the participating patient on the importance of maintaining the assigned visit schedule and ascertain whether or not the participating patient wishes to and/or should continue in the study.
- Before a participating patient is deemed lost to follow up, the investigator or designee must make every effort to regain contact with the participating patient (where possible, 3 telephone calls and, if necessary, a certified letter to the participant's last known mailing address or local equivalent methods). These contact attempts should be documented in the participant's medical record.
- Should the participant continue to be unreachable, he/she will be considered to have withdrawn from the study.

Discontinuation of specific sites or of the study as a whole are handled as part of Appendix A.

8 STUDY ASSESSMENTS AND PROCEDURES

The Electronic Data Capture (EDC) system will be used for data collection and query handling. The Investigator will ensure that data are recorded on the electronic Case Report Forms (eCRF) as specified in the study protocol and in accordance with the instructions provided.

Except for the questionnaires to be completed by participants (see SOA), all data will be based on what have been generated during routine clinical practice. Data collection for all enrolled patients will follow up version 2.0.

Baseline data collection

At baseline visit (V0, week -12), the following patient data will be collected from patients:

- Demographic information

- Vital signs include body mass index
- Subject Status
- Asthma history, comorbidities, and medications (historical data)
- Laboratory and clinical testing within 3 months (if available in medical records), including CBC with differentiation, blood gas analysis (pH, SaO₂, PaO₂, PaCO₂, and HCO³⁻), C-reactive protein, skin allergen prick, total IgE or specific IgE, PFT (pulmonary function testing), BPT (bronchial provocation test), PEF (peak expiratory flow) and FeNO (fractional exhaled nitric oxide)
- Current visit asthma treatment information
- Two patient-reported outcomes (PRO) questionnaires (ACQ-5 and AQLQ(S)+12)
- MARS-A questionnaire
- Questionnaire of asthma knowledge for patient
- Inhale skill score for patient
- Patient's expectation for asthma treatment

Follow up data collection

After the initiation of the intervention program, participants will return to the study hospital every 12 weeks for on-site follow-up visits (V1 to V5), in accordance with guideline recommendation. During on-site visits, the usual care activities can be performed as needed.

Participants are encouraged to come back to the study hospital if they have asthma-related conditions or symptoms worsening. If in emergency case, they can choose to visit a hospital other than the study hospital, and they should report it to study pulmonologists or study staffs once it is possible. In case there are data generated from other hospitals that need to be collected as per protocol, i.e. hospitalization due to exacerbation, the data and supportive documents (e.g., medical record of hospitalization summary) will be required at next on-site visit.

At follow-up visits (V1 to V5), the data generated from usual care activities after the initiation of the intervention will be collected from patients, including severe asthma exacerbation, asthma-related hospitalizations, emergency attendances, and outpatient visits, and medications.

In addition, two PRO questionnaires (ACQ-5 and AQLQ(S)+12) will be administered to participants at site at each visit and be entered by study personnel into the EDC system. MARS-A questionnaire, Questionnaire of asthma knowledge for patient, Inhale skill score for patient,

Patient's expectation for asthma treatment will also be administered.

The schedule of assessments and procedures are summarized in Table 1.

